#### 2.5.3 AF Recurrence

The primary endpoint will evaluate recurrence of AF during the 9 months following the blanking period for each group. Secondarily, the recurrence of AF based on electrocardiographic data at 3 months, 6 months and 24 months post procedure will also be reported by group. The rate of AF recurrence will be calculated using the same definition as the primary objective for the specified time points.

 Assessment of the AF recurrence will be determined through evaluation of 12 lead ECG recordings, holter monitoring or event recorder results. AF Recurrence is defined as episodes lasting longer than 30 seconds in duration unless detected via 12 Lead EKG. To count as a study-related recurrence, the AF episode must be documented. For this study, AF recurrence also includes (documented ≥30 seconds) atrial flutter and atrial tachycardia.

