	Subject has blood clotting or bleeding abnormalities
	Subject has secondary arterial hypertension

Table 1. Study Evaluations

Study Activity	Enrollment / Baseline*	Procedure ≤30 days after Enrollment	Discharg e <72 hrs	1M ±7d	3M ±10d	6M ±14d)	12M ±21d	24M ±60d
Consent Process	Х							
Inclusion/Exclusion	Х							
Medical and Cardiovascular History	Х							

Study Activity	Enrollment / Baseline*	Procedure ≤30 days after Enrollment	Discharg e <72 hrs	1M ±7d	3M ±10d	6M ±14d)	12M ±21d	24M ±60d
12-Lead ECG	X	Х	X	Х	Х	Х	Х	Х
Office Blood Pressure	Х			Х	Х	Х	Х	Х
Physical Assessment	Х			Х	Х	Х	Х	Х
24-h Ambulatory Blood Pressure	X-performed w/in 90 days prior to procedure					X	Х	X
Discharge Blood Pressure			Xp					
Echocardiography (TTE)	х			x		Х	X	х
NYHA Assessment	Х			Х		Х	Х	Х
Serum creatinine	Х					X ^t	X ^t	X ^t
Estimated GFR	Х					X ^t	X ^t	X ^t
Hemoglobin A1c	Х					X ^t		
Fasting Glucose	Х					X ^t		
Fasting Insulin	Х					X ^t		
Urine albumin-to- creatinine ratio	Х					X ^t		X ^t
Quality of Life Assessment (EQ-5D 5L & AFEQT)	х			х		Х	х	Х
Renal Artery Anatomy Evaluation	X ^t					X ^t	X ^t	
Pregnancy Test (urine / blood)	X							
Renal Denervation Procedure		X ^t						
Cardiac Ablation Procedure		Х						
7 Day Holter or Event Monitor			Х		Х	Х	х	Х
Medications	Х	Х	Х	Х	Х	Х	Х	Х
Adverse Event	**	**	**	**	**	**	**	**
Protocol Deviation	**	**	**	**	**	**	**	**
Withdrawal/ Termination		**	**	**	**	**	**	**

SJM CONFIDENTIAL AND PROPRIETARY

- (*) Baseline tests and procedures must be performed within 90 days of Enrollment
- (**) as applicable
- (b) monitored every 4 hours post procedure until discharge, or for a maximum of 24 hours
- (t) only applicable to patients who are in the renal denervation randomization group

2 Background

Hypertension or high blood pressure is a major risk factor for cardiovascular and cerebrovascular events. ¹⁻³ It is responsible for approximately one half of the coronary heart disease and two thirds of the cerebrovascular disease burdens. ⁴ It is also the world's number one attributable risk for death. The global prevalence of hypertension has been increasing. An analysis indicated that more than one quarter (nearly one billion) of the world's adult population had hypertension in 2000. This is projected to increase to 1.56 billion affected individuals with a prevalence rate of 29% in 2025. ⁵ This is a major public health challenge in both economically developing and developed countries.

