4.6 Blanking Period

For three months following the ablation procedure, the subject is in a blanking period while the cardiac tissue recovers from the RF energy application. The AF recurrences during the blanking period will not be reported. If recurrence occurs after the blanking period, the subject will be considered a 'recurrence' according to the primary efficacy endpoint.

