4.10.10 Assessment of AF Recurrence

Assessment of AF Recurrence will be completed at the 3M, 6M, 12M and 24M follow-up visits viaevaluation of 12 lead ECG recordings, holter monitoring and/or event recorder results. Subjects will be provided 7-day holter monitors for each of these visits or implanted with an event recorder which will be evaluated for the specific 7 day period coinciding with a visit. AF recurrence will not be counted within a 3 month blanking period following the cardiac ablation procedure.

AF Recurrence is defined as episodes lasting longer than 30 seconds in duration. To count as a study-related recurrence, the AF episode must be documented. For this study, AF also includes (documented ≥30 seconds) atrial flutter and atrial tachycardia.

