#### 2.4 Primary objective

The primary objective is to assess the feasibility of concomitant cardiac ablation for the treatment of atrial fibrillation and renal denervation ablation using the EnligHTN renal denervation system in achieving freedom from atrial fibrillation in patients with hypertension.

Project Code: SJM-CIP-0009 Project Name: RD+AF

The freedom from atrial fibrillation will be assessed based on electrocardiographic data during nine months following the blanking period including the one week recording coinciding with the 12 month follow-up visit (9 months following the 3 month blanking period). AF recurrence during the blanking period will not qualify as an endpoint event per protocol. Subjects may be re-treated with up to two repeat ablation procedures during the course of the study with a 3 month blanking period following the treatment. Assessment of the AF recurrence will be determined through evaluation of 12 lead ECG recordings, holter monitoring or event recorder results. AF Recurrence is defined as episodes lasting longer than 30 seconds in duration unless detected via 12-lead EKG. To count as a study-related recurrence, the AF episode must be documented on the AF Recurrence Evaluation CRF. For this study, AF also includes (documented >30 seconds) atrial flutter and atrial tachycardia.

No formal hypothesis testing will be performed. An overall percentage of subjects experiencing an event will be summarized for each randomization arm and is defined as:

Number of subjects with AF recurrence within 12 months post procedure Number of subjects with at least 12 months of follow – up or experienced AF recurrence \* 100

Subjects who exit the study prior to 12 month visit without AF recurrence will be excluded from the percentage to prevent under-estimation of the event rate. Kaplan-Meier analysis may be performed to provide freedom from atrial fibrillation rates at one year for each randomization arm using date of ablation procedure to date of first event.

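### The 3-month AF recurrence rate is to use the primary definition, which excludes the first 3 months: read literally, the ECG-based rate is 0% in both arms, and the other readings conflict with the text or depend on visit timing

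*SAP*

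**What the plan says.** SAP 2.5.3 (AF Recurrence) lists the secondary recurrence results: "the recurrence of AF based on electrocardiographic data at 3 months, 6 months and 24 months post procedure will also be reported by group". The next sentence gives the rule: "The rate of AF recurrence will be calculated using the same definition as the primary objective for the specified time points". Protocol 7.4.2.3 lists the same three time points.

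The primary definition is in SAP 2.4. Its numerator and denominator run from the procedure to 12 months, and it adds that "AF recurrence during the blanking period will not qualify as an endpoint event per protocol". The protocol fixes the length and start of blanking in 4.6: "For three months following the ablation procedure, the subject is in a blanking period". Three places in the protocol say what happens to episodes in that period:

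- 4.6: "The AF recurrences during the blanking period will not be reported".
- 4.10.10: "AF recurrence will not be counted within a 3 month blanking period following the cardiac ablation procedure".
- 7.4.1 repeats the not-counted rule for the primary objective.

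The protocol also treats 3 months as a recurrence time point. Section 4.10.10 says "Assessment of AF Recurrence will be completed at the 3M, 6M, 12M and 24M follow-up visits", and Table 1 schedules a 12-lead ECG and the item "7 Day Holter or Event Monitor" at the 3-month visit, which has a window of ±10 days. Separately, protocol 4.8 counts repeat ablation towards recurrence and states no exception for the first three months.

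**The concern.** The 3-month cut-off and the end of blanking are the same date, measured from the same ablation. A rate that ignores everything in blanking and stops when blanking ends has no ECG time in which an event can count.

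An analyst who programs SAP 2.5.3 as written would report 0% against 0%. A reader could take that as absence of early recurrence when it reflects only the counting rule. Another analyst could reasonably decide that an early-recurrence figure was meant and report something quite different from the same data. The trial is descriptive, with no hypothesis test, so its summaries are its product and each needs a single meaning. What is at stake is one secondary time point.

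**Working it through.** **Inputs**

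- Time points: 3, 6 and 24 months post procedure (SAP 2.5.3, protocol 7.4.2.3); 12 months for the primary (SAP 2.4).
- Blanking: 3 months from the ablation (protocol 4.6, 4.10.10, 7.4.1).
- Rate at time T: subjects with recurrence within T, divided by subjects followed to T or with recurrence (SAP 2.4, with T in place of 12 months).
- 3-month visit window: ±10 days (protocol Table 1 and 4.10).

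**Step 1: reproduce the plan's own figure.** For a subject not re-treated, countable months = T − 3. For the primary endpoint, 12 − 3 = 9, which matches the nine months in SAP 2.4.

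**Step 2: apply the same formula to the secondary time points.**

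| Time point | Countable months |
|---|---|
| 3 | 3 − 3 = 0 |
| 6 | 6 − 3 = 3 |
| 24 | 24 − 3 = 21 |

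Only the 3-month time point is empty.

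**Step 3: the literal rate.** With no countable time, the ECG-based numerator is 0. Assuming an exact 2:1 split and full follow-up to 3 months, the rates are 0/50 and 0/25 with the SAP's 75 patients, or 0/67 and 0/33 with the protocol's 100. Both arms give 0%.

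**Step 4: the route not based on ECG.** A repeat ablation within 3 months could enter an overall numerator through protocol 4.8. The zero therefore applies to the ECG-based rate that SAP 2.5.3 names, and not necessarily to every way of counting recurrence.

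**Step 5: the visit reading.** Let v be the visit day relative to the end of blanking, with v = −10 to +10, so 21 allowed days. A day is countable if it falls after day 0.

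- 12-lead ECG at the visit: countable only if v > 0, which is 10 of 21 days.
- 7-day recording ending on the visit day (days v − 6 to v): some of it is countable only if v > 0, again 10 of 21 days.
- 7-day recording starting on the visit day (days v to v + 6): some of it is countable if v + 6 > 0, so v = −5 to +10, which is 16 of 21 days.

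Protocol 4.10.10 says that the recording coincides with the visit but not whether it starts or ends there. These are counts of allowed calendar days; they do not estimate how many subjects would be affected.

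**Step 6: the formula-only reading.** If blanking is not applied at 3 months, the rate is the share of subjects with documented AF in months 0 to 3. The documents do not give that share. If it were anywhere from 10% to 60% (an assumed range), the reported figure would be 10% to 60% instead of 0%.

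**The case against.** The strongest reply is that the phrase about the same definition attaches to the rate. In SAP 2.4 the explicit definition is the percentage formula. Blanking is a separate, earlier sentence, worded in terms of what qualifies as an endpoint event. SAP 2.5.3 and protocol 7.4.2.3 both restate what counts as recurrence without repeating the blanking rule, whereas protocol 7.4.1 includes it. Protocol 4.6 also links recurrence after blanking to the primary efficacy endpoint. With a recurrence assessment, an ECG and a 7-day recording scheduled at 3 months, a descriptive early-recurrence figure may well have been intended.

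This reading is possible, and it stands as a reason not to call the zero inevitable. It does not clear the text. The SAP never limits the phrase to the formula, and an unblanked 3-month figure contradicts protocol 4.6, under which such recurrences go unreported, and 4.10.10, under which they go uncounted.

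A second reply is that the primary definition is partly visit-based, because it includes the week of recording around the 12-month visit. Carried over to 3 months, it would take in the recording around the 3-month visit, part of which can fall after blanking. That is fair. But SAP 2.5.3 sets its time points post procedure, and the visit reading gives a quantity governed by scheduling, not 3-month recurrence.

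A reader might infer that the rule gives 0% in both arms whatever the data. The documents do not support that. Protocol 4.8 leaves repeat ablation as a possible early event, and the visit and formula-only readings could each give a non-zero rate.

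Finally, the impact is small: one descriptive time point in a study without hypothesis tests, with the blanking rule stated in several places. That limits the weight of the point but not the need to settle it.

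**Conclusion.** The point holds in a limited form. At 3 months post procedure, under the primary definition, no ECG-documented episode can count, so the ECG-based rate is 0% in both arms. This is the literal result of the stated rule and not the only possible result. An overall rate could be non-zero through a repeat ablation within 3 months. The visit reading makes countable recording possible on 10 or 16 of the 21 allowed visit days, for a recording that ends or starts on the visit day respectively. The formula-only reading gives a real early-recurrence figure, but one that conflicts with protocol 4.6 and 4.10.10.

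The conclusion assumes that the time point is measured from the ablation, as SAP 2.5.3 says, and that blanking belongs to the primary definition, as SAP 2.4 indicates. The effect is confined to this one descriptive secondary result. The primary, 6-month and 24-month rates are unaffected. The correction is worth making before analysis because it is cheap and the present text permits different answers.

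**What to change.** In SAP 2.5.3 and protocol 7.4.2.3, remove 3 months from the time points that use the primary definition. Then choose one of two options.

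1. **Drop the 3-month result.** This needs wording changes in those two sections only, with no change to data collection.
2. **Keep it as a separately labelled descriptive summary by arm.** Suggested definition: subjects with a documented qualifying episode within 3 months of ablation, divided by subjects followed to 3 months or with such an episode; not an endpoint failure. State whether a repeat ablation counts in it. Reconcile protocol 4.6 and 4.10.10 so that blanking-period episodes are recorded while still not counting as recurrence for the primary endpoint.

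The second option depends on the AF Recurrence form capturing blanking-period episodes. Protocol Appendix H provides the form's data points under separate cover, so this cannot be checked here; sites may have to record more and the form may need a small change. Neither option alters the primary endpoint.

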#### 2.5.4 BP reduction

The mean reduction of office systolic BP, office diastolic BP, and ambulatory BP parameters at six (6) months will be analyzed by computing the reduction of BP measurements compared to baseline (6-month – baseline) for each patient with data available in both time points. The mean and standard deviation of the BP reduction will be summarized for each group.

Blood pressure parameters at 12 and 24 months post procedure will be calculated in the same way as described in the calculation of the reduction at 6 months.

The percentage of subjects achieving office SBP < 140 at 6 months visit will be computed for each group as follows:

Number of subjects achieving office SBP < 140 at 6 months visit \*100

Number of subjects with data available in 6 months visit

#### 2.6 Other Analyses

In addition, subgroup analyses may be performed as needed, e.g.:

- for subjects that have the renal denervation procedure performed on one side but not the other (due to their anatomy, circumstances related to the procedure, or physician judgment)
- based on the number of ablation points performed
- by the subject's primary disease conditions at baseline.

Ad hoc analyses may be performed as needed. Analysis may be performed based on As Treated population as appropriate. In general, data analysis will be performed on a per subject basis, but the data analysis may be presented per kidney, or on renal artery basis, as appropriate.

#### 2.7 Analysis Software

The statistical analyses will be performed using SAS™ software version 9.3, or as specified and appropriate.
